[#] If one of the three collected MGIT cultures is contaminated rather than negative, this will be considered acceptable, provided that the remaining two MGIT cultures are negative and all three sputum Xpert results are also negative

PROTOCOL SUMMARY

Title	Asymptomatic Tuberculosis Transmission in Indonesia and South Africa
Short Title	ATTIS Study
Protocol number	A-ATTIS-001
Settings	Contiguous geographical areas (study areas) in King Cetshwayo and uMkhanyakude Districts, KwaZulu-Natal, South Africa and Bandung City, Indonesia
Study Duration	30 months
Summary of Approach	
This is a cross-sectional study comparing the Mtb infection status in child household contacts of people with asymptomatic TB, people with symptomatic TB and community controls (core study). These households will be identified through community-based TB screening.
 
A case-control phenotyping study (sub-study 1) will be conducted on participants classified as aTB-C, sTB-C and noTB and will include additional diagnostic tests, clinical phenotyping and biobanking.
 
A TB-Unconfirmed cohort (sub-study 2) study will be conducted on participants with bacteriologically-unconfirmed TB (TB-U) that does not meet criteria for TB treatment and will include serial clinical evaluation, diagnostic testing and biobanking.
 
A mathematical modelling study (sub-study 3) will utilise empiric data from the study to estimate the contribution of asymptomatic TB to local and global TB transmission and incidence and the impact of potential interventions.

Co-primary Objectives	Compare Mtb infection, as defined by interferon release assay (IGRA) positivity, in child household contacts (2 to 14 years) of adults with bacteriologically-confirmed asymptomatic TB (aTB-C), with: 
 (1) children in households with no adult with TB (2) children who are household contacts of adults with bacteriologically-confirmed symptomatic TB (sTB-C).
Secondary Objectives	
 (1) Evaluate the diagnostic performance, feasibility and acceptability of current diagnostic tools to detect aTB, including digital chest x-ray with computer aided diagnosis (dCXR/CAD), sputum Xpert, and sputum Mycobacteria Growth Indicator Tube (MGIT). (2) Evaluate the performance of novel diagnostic and screening tools to detect aTB including tongue swab NAAT, bioaerosol NAAT, exhaled breath

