non-sputum diagnostic tools⁶¹. These assays rely on stimulating whole blood or PBMC with *M. tuberculosis* antigens and measuring upregulation or loss of surface markers such as CD38, HLA-DR and CD27 on Mtb-specific T cells. Studies have shown that the presence of the MTB-specific activated T-cells indicates infection (latent or active, depending on clinical context).

However, larger evaluations are still needed to validate their performance, particularly in aTB.

MTB CELL FREE DNA

There is growing interest in blood-based (non-sputum) approaches that can detect fragments of circulating *Mycobacterium tuberculosis* as complementary or alternative diagnostic biomarkers. CRISPR-mediated detection platforms have emerged as promising tools due to their ability to amplify and detect short, low-abundance Mtb cfDNA fragments with high analytical sensitivity, potentially enabling non-sputum diagnosis and earlier detection⁶².

Several studies have demonstrated that Mtb cell free DNA (cfDNA) can be recovered from plasma and detected by CRISPR-based assays, where Cas12a complexes generate enzymatic signal amplification to improve detection of low concentrated target sequences. Huang et al, reported high diagnostic accuracy of Mtb cfDNA, with sensitivity of 96% (80-100) and specificity of 94% (71-100) in microbiologically and clinically confirmed HIV-negative TB cases, and sensitivity of 83% (36-100) and specificity of 95% (77-100) in paediatric and extrapulmonary cases. These findings support the potential Mtb cfDNA CRISPR-mediated assay as a rule-in test or as an adjunct to existing workflows.

Critical questions remain regarding their performance in detecting bacteriologically-confirmed aTB and whether they may be able to improve specificity and provide bacteriologic confirmation in people who would otherwise meet the definition of aTB-U.

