		
3. Participants selected as healthy controls
 
Inclusion criteria
 
 1. Adolescent/adult participant in TB screening 2. Screening W4SS negative 3. Screening sputum Xpert negative; AND Mtb MGIT negative* 4. Selected as a healthy control in the Cross-sectional study of Mtb infection in households (see above) 
ALL 3 groups above
 
Exclusion criteria
 
 1. Unable or unwilling to consent 
* MGIT results returning after enrolment may result in study group re-categorisation

Cohort study (sub-study 2)	Adolescents and adults (≥ 15 years) who participated in TB screening.	
Participants who meet the study case definition for bacteriologically-unconfirmed TB (TB-U)
 
Inclusion criteria:
 
 1. Adolescent/adult participant in TB screening 2. All three sputa Xpert are negative/ ‘trace’ AND all three sputum are Mtb MGIT negative 3. Screening dCXR/CAD interpretation is “suggestive of TB” 4. Clinical assessment at phenotyping visit does not suggest a non-TB aetiology for dCXR/CAD findings and is consistent with TB-U 5. Participant did not commence TB treatment after phenotyping visit 
Exclusion criteria
 
 1. Unable or unwilling to consent to longitudinal follow-up

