In addition, a digital chest X-ray with computer-aided detection (dCXR/CAD) will be conducted as part of the TB screening assessment. All dCXR/CAD X-Rays which are reported as suggestive of TB by the CAD software will be reviewed by a radiologist.

Within 2 weeks of the screening visit (visit 1.0), the **adolescent/adults** screened will be categorised into one of 5 screening groups ([Figure 2](#)).

- (1) **aTB-C Participant:** W4SS screening - negative; Xpert -positive (any grade) OR tongue swab-NAAT – positive; dCXR/CAD – any result
- (2) **sTB-C Participant:** W4SS screening - positive; Xpert -positive (any grade) OR tongue swab-NAAT – positive ; dCXR/CAD - any result
- (3) **aTB-U Participant:** W4SS screening - negative; Xpert -negative-OR tongue-swab NAAT – negative; dCXR/CAD – suggestive of TB
- (4) **sTB-U Participant:** W4SS screening -positive; Xpert-negative OR tongue-swab NAAT – negative; dCXR/CAD – suggestive of TB
- (5) **noTB Participant:** W4SS screening -negative; Xpert – negative OR tongue swab NAAT – negative ; dXR/CAD – normal

Adult and adolescent participants (≥15 years) will be identified ([Figure 2](#)) for potential enrolment into either the case-control phenotyping-study (Sub-study 1; aTB-C, sTB-C) or the TB-U cohort study (Sub-study 2; TB-U). For each aTB-C participant, a control participant (1:2 ratio) will be randomly selected among noTB participants within the neighbourhood (250–700 m radius depending on the population density, using GIS coordinates) of the aTB-C participant's household.

The **child household contacts (aged 2–14 years)** of those with aTB-C and their controls, and sTB-C will be eligible for inclusion in the cross-sectional study (IGRA assessments) of household Mtb infection (core study).

[figure not shown]

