A community, or clinic-based follow-up visit or telephonic contact will be conducted between weeks 2 and 14 (**Visit 2.3**) for participants with positive results. This visit will be used to provide IGRA and sputum results (where sputum was collected) and to confirm that appropriate referral to the local health clinic for TPT initiation or TB treatment, as indicated, has occurred. The study team will provide support to strengthen local health care facilities by building capacity in the provision of TPT for household contacts of participants diagnosed with TB, in accordance with national guidelines.

In South Africa, HIV results will be provided with post-test counselling using language appropriate to the child's age and maturity. Children aged 12–14 years may receive their results without a parent or guardian present but will be encouraged to involve their parent or guardian in the discussion and ongoing support.

Participants with negative results will be contacted via telephone or SMS. This visit will mark the End-of-Study visit for household contacts.

SUB-STUDIES 1 and 2

Within two weeks of TB screening, eligible participants will be invited to attend the research clinic for **Visit 1.1**. Participants will remain blinded to their screening results at the time of the visit. At Visit 1.1,

individual consent or assent will be obtained for participation in the sub-studies. This visit will include all participants being enrolled in either Sub-study 1 (aTB-C, sTB-C, and control participants) or Sub-study 2 (TB-U participants).

At the clinic, a **blinded structured questionnaire** will be administered to collect detailed information on symptoms, quality of life, functional status, and health outcomes. This will be followed by a comprehensive physical examination, including assessment of vital signs, height, weight, lymphadenopathy, and breath sounds. Two samples, either an early-morning and spot specimen or two spot specimens, as per site procedures will be collected for Xpert and MGIT culture testing. Participants whose screening molecular test was a positive tongue swab NAAT, will have 3 sputum specimens collected.

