Table 4: Minimum risk difference that can be detected in each site with 80% power, comparing aTB and control households

Number aTB cases	Number controls ¹	Mean children per HH	ICC	% IGRA positive in control HH	% IGRA positive in aTB HH	Risk difference ²	Power
Indonesia							
150	300	1.5	0.30	20%	32%	12%	80%
South Africa							
150	300	2.5	0.30	7%	14%	7%	80%

¹Number of control households. ²Absolute difference = proportion of children IGRA+ in aTB households minus proportion of children IGRA+ in control.

For our second co-primary objective, we have used the risk ratio (relative risk) as the effect estimate of interest, because the duration of exposure for children in aTB-C and sTB-C households is expected to be similar. For policy decisions, it would be useful to know that the transmission risk of aTB-C is not substantially lower than that of sTB-C; therefore, we have used a non-inferiority approach for our power calculations. We have assumed that the prevalence of IGRA positivity in children in sTB-C households is 40% in Bandung and 18% in KwaZulu Natal (our best estimates, based on available data). With 150 sTB-C and 150 aTB-C index cases, we will have at least 80% power in each setting to demonstrate that the transmission risk with aTB-C is not less than 50% compared with that of sTB-C, assuming that the true risk ratio (RR) is at least 0.90 ([Table 5](#)).

Table 5: Relative reduction that can be excluded with 80% power, comparing aTB and sTB households¹

Number sTB cases	Number aTB cases	% IGRA positive in sTB HH	% IGRA positive in aTB HH	Risk ratio (aTB/sTB)	Relative reduction that can be excluded ²
Indonesia - aTB vs sTB					
150	150	40%	28%	0.70	0.46
150	150	40%	32%	0.80	0.55
150	150	40%	36%	0.90	0.63
South Africa - aTB vs sTB					
150	150	18%	12.6%	0.70	0.43
150	150	18%	14.4%	0.80	0.49
150	150	18%	16.2%	0.90	0.55

¹Assuming ICC=0.30. ²Lower limit of 95% confidence interval for risk ratio

CASE-CONTROL STUDY (SUB-STUDY 1)

The case-control study will enrol 150 aTB-C and 150 sTB-C cases, and 300 community controls with no TB. Assuming that the true sensitivity and specificity of the Plus Life tongue swab and bioaerosol collection facemask diagnostic tools are between 70-95%, with 150 aTB-C and 150 sTB-C cases, we will be able to estimate the sensitivity with a precision of $\pm 7.6\%$ to $\pm 4.0\%$. With 300 controls, we will be able to estimate the specificity with a precision of $\pm 5.3\%$ to $\pm 2.6\%$.

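### Novel-tool specificity for aTB-C is planned only in controls with a normal X-ray; sputum-negative people with a suggestive X-ray give the same samples but do not enter the estimate

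*Protocol*

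**What the plan says.** **Who is in the accuracy analysis.** The Protocol Summary says that the phenotyping study (sub-study 1) "will be conducted on participants classified as aTB-C, sTB-C and noTB". Section 5.1 gives the numbers: "The case-control study will enrol 150 aTB-C and 150 sTB-C cases, and 300 community controls with no TB". Sensitivity, specificity and predictive values appear only under sub-study 1 (Sections 3.8 and 5.2).

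**Which people carry specificity.** Section 5.1 states: "With 300 controls, we will be able to estimate the specificity with a precision of" ±5.3% to ±2.6%, for true values that "are between 70-95" percent. Controls are drawn at random from noTB participants near each aTB-C household. Section 3.5 defines noTB as "W4SS screening -negative; Xpert – negative OR tongue swab NAAT – negative ; dXR/CAD – normal".

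**Who else takes the tests.** For Visit 1.1, Section 3.5 says: "This visit will include all participants being enrolled in either Sub-study 1 (aTB-C, sTB-C, and control participants) or Sub-study 2 (TB-U participants". Table 2 and Section 3.5 list tongue swab, facemask, exhaled breath condensate, and blood for cell-free DNA and T-cell activation at that visit, without separating the two sub-studies.

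**Who enters the cohort.** Table 1 requires three sputa that are Xpert negative or trace and MGIT-negative, a suggestive X-ray, no TB treatment started, and this: "Clinical assessment at phenotyping visit does not suggest a non-TB aetiology for dCXR/CAD findings and is consistent with TB-U".

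**The question raised.** On the cell-free DNA assay, Section 1 asks "whether they may be able to improve specificity and provide bacteriologic confirmation in people who would otherwise meet the definition of aTB-U".

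**The concern.** Specificity depends on which people without the target condition are tested. Section 1 says that an abnormal X-ray in a sputum-negative person may reflect early TB, old treated TB or non-TB disease. It also says that tongue swab performance varies greatly with the population studied. Controls chosen for a normal X-ray and no symptoms leave out everyone with old scars or other lung disease, and false positives are most plausible in those people. This is spectrum bias, and its likely direction is towards a flattering estimate.

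At stake is one high specificity figure being read as applying to people with abnormal X-rays. Section 1 asks about specificity in that group for cell-free DNA. The samples that could address it are taken at Visit 1.1.

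**Working it through.** **1. The plan's own figure.** The exact (Clopper-Pearson) 95% interval for x negatives among n has lower limit Beta(0.025; x, n−x+1) and upper limit Beta(0.975; x+1, n−x). The half-width is half the distance between them.

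| n | True value | x | Half-width (points) | Section 5.1 |
|---|---|---|---|---|
| 300 | 70% | 210 | 5.33 | 5.3 |
| 300 | 95% | 285 | 2.64 | 2.6 |
| 150 | 70% | 105 | 7.61 | 7.6 |
| 150 | 95% | 142 | 3.95 | 4.0 |

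All four stated figures reproduce. The arithmetic is right, and the specificity denominator is the 300 controls and nobody else.

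**2. Status of the X-ray-suggestive group.** The case definition of aTB-C needs an Xpert result above trace or a positive MGIT on at least one of three sputa. A symptom-negative person with three MGIT-negative sputa and Xpert negative or trace throughout meets neither condition. That person is target-negative for aTB-C even when the X-ray is suggestive.

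**3. What the plan does with them.** Outcome 9 (Section 3.8) reports the proportion of people with screening results suggestive of TB-U who later have a positive sputum, tongue swab or facemask test. It does not list cell-free DNA. Outcome 8 relates plasma biomarkers, including cell-free DNA, to progression. Neither sets Visit 1.1 results against sputum status as a specificity.

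**4. Precision available.** Section 5.1 expects 500 cohort participants per site, and the Protocol Summary describes them as aTB-U. By the same exact method:

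- 70% specificity (x = 350): 4.11 points.
- 95% specificity (x = 475): 2.02 points.

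This stratum alone would be more precise than the controls. Section 5.1 expects 31 to 66 progressors per site. Removing them leaves 500 − 66 = 434 to 500 − 31 = 469, before trace results and treatment starts are taken out.

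**5. Illustration, with assumed values.** Suppose a tool with 70% sensitivity is used after a suggestive X-ray, and that 500 people per site have such an X-ray without aTB-C. The number with aTB-C and a suggestive X-ray is uncertain:

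- 150 × 0.47 = 70.5, from the contact study in Section 1 in which 47% had an abnormal X-ray. The TB share is 70.5/570.5 = 12.4%.
- 150, if the X-ray-positive label in Table 3 is taken at face value. The TB share is 150/650 = 23.1%.

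PPV = true positives / (true positives + false positives):

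| Assumed specificity | False positives per 500 | PPV, 12.4% share | PPV, 23.1% share |
|---|---|---|---|
| 95% | 25 | 49.35/74.35 = 66% | 105/130 = 81% |
| 90% | 50 | 49.35/99.35 = 50% | 105/155 = 68% |

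Five points of specificity double the false positives. The protocol does not say which specificity applies to this group.

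**The case against.** **These participants are not unused.** A reader might infer that TB-U participants belong to no analysis, or that nothing is planned on test positivity in them. The protocol does not support that. Outcome 9 takes screening TB-U as its denominator, so it also covers people later judged to have a non-TB cause, and it reports tongue swab and facemask positivity. Outcome 8 covers the plasma biomarkers. What is missing is narrower: specificity against sputum status, and cell-free DNA in outcome 9.

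**aTB-U is a TB category here.** Section 1 stresses that sputum tests miss paucibacillary disease, and it cites mask-positive, sputum-negative people of whom half later became Xpert-positive. A positive novel test in this group may be early detection. This stands. It rules out treating serial sputum as proof of no TB and rules out simple pooling with controls. It does not remove the need for the stratum, because the target of the accuracy analysis is aTB-C, which is defined by sputum.

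**The Section 1 question concerns cell-free DNA only.** Correct. It should not be read as a stated aim for every tool. The case for the other tools rests on secondary objective 2, which evaluates them for aTB generally.

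**Community controls suit universal screening.** They are relevant to that use and should stay. They do not describe use in people with an abnormal X-ray.

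**The SAP could add the cross-tabulation.** It could, and it is not at hand. But the protocol itself fixes the specificity group and its size.

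**Two loose ends in the documents.** Table 1 lists no X-ray criterion for healthy controls; the normal X-ray comes from the noTB definition. Appendix C heads Visit 1.1 under sub-study 1 alone, whereas Table 2 and Section 3.5 cover both sub-studies.

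**Conclusion.** The point holds as a limit on whom the planned specificity describes. The estimate rests on 300 symptom-negative, X-ray-normal controls per site and is likely too favourable for people with abnormal X-rays. A target-negative group with suggestive X-rays gives the same samples at the same visit and does not enter it.

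The available precision is about 4.1 to 2.0 points for 70% to 95% specificity. It assumes about 500 evaluable people per site. That is the expected cohort size, so it does not count people judged to have a non-TB cause. The number shrinks if some cohort members are symptomatic.

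The size of the bias cannot be derived from the documents. The PPV range of 50% to 68% at 90% specificity and 70% sensitivity is an illustration resting on assumed accuracy and an uncertain TB share. It is tempting to conclude that specificity is known to fall by a given amount in this group. The documents do not show that, and Section 1 reports very high oral-swab specificity across studies.

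**What to change.** In Section 5.2, sub-study 1, add a second specificity stratum:

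- **Who:** participants with a negative four-symptom screen and a suggestive screening X-ray.
- **What:** Visit 1.1 results of each novel tool, including cell-free DNA and T-cell activation, against three-sputum status as the reference.
- **How reported:** beside the X-ray-normal controls and not simply pooled with them, split into those judged to have a non-TB cause and those consistent with aTB-U.
- **Sensitivity analysis:** exclude trace Xpert results and participants who progress or start treatment by month 12.
- **Label:** state that specificity here is a lower bound, because some participants may have TB that sputum missed. Mark any PPV illustration as assumed.

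The cost is analysis wording and reporting. No visit, sample or participant is added. The main stratum can be reported once the Visit 1.1 cultures are final; the sensitivity analysis waits for month 12.

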3.5 STUDY PROCEDURES

Large scale community screening will be conducted among adolescents and adults aged 15 years and older who reside in the study areas and in households (HH) with children aged 2–14 years. To better understand Mtb transmission, households will be enrolled from contiguous geographic areas, allowing for the assessment of transmission while minimising geographic variability and potential confounding introduced by non-adjacent areas.

Prior to entering each selected area, the study team will obtain permission from the local area leader or community authority. Study areas will be mapped using Quantum Geographic Information System (QGIS) software or other equivalent geographic information system tools to define boundaries and identify households for enumeration. All households within these contiguous areas will be visited to enumerate inhabitants (**Figure 2**). Household enumeration will be part of visit 0 and may be done on the same date as visit 1.0. Informed consent will be obtained from the household head before any study activities are conducted. Following consent, household enumeration will be performed to determine eligibility for participation, and minimal dwelling characteristics will be recorded. The GPS coordinates of participating households will also be documented as part of the household-level assessment.

Figure 2. Schematic overview of participant flow across study components

At the **screening and enrolment (visit 1.0)**, all adolescent and adult household members will be approached for informed consent/ assent. Following enrolment, demographic information and responses to a basic health questionnaire will be collected. Participants will undergo symptom

screening using W4SS. They will also answer a question about the presence and nature of any additional symptoms they are experiencing, and whether any of their symptoms have prompted them to seek health care. A minimal physical examination, including measurement of weight and height, will be performed. Following coaching, each participant will provide a minimum of 3ml sputum/respiratory tract sample for Xpert and MGIT culture testing

If following coaching, the participant is still unable or refuses to produce a 3ml sputum sample, a tongue swab will be collected for NAAT. Tongue swabs will only be collected if their programmatic use has been approved by WHO and/or national authorities (South Africa or Indonesia), and in participants unable or refuse to produce sputum.

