Eligible participants for this TB-U cohort study will be evaluated in the research clinic every three months (month 3,6,9 &12) for one year (**Visits 1.2-1.5**) to monitor progression.

At each follow-up visit, participants will undergo a structured clinical assessment, including an interim health history, review of recent antibiotic or TB treatment use, detailed symptom screening, evaluation of quality of life, functional status, and health-seeking behaviour.

A comprehensive physical examination will be performed, including assessment of vital signs, height, weight, lymphadenopathy, and breath sounds.

Sputum specimens will be collected for TB phenotyping, consisting of two samples, either an early-morning and spot specimen or two spot specimens, as per site procedures. Venous blood will be drawn for phenotyping assays, including Mtb-specific T cell activation, Mtb cell-free DNA, and samples for biobanking. A dCXR/CAD will be performed at each visit. Facemask and Exhaled breath condensate will be collected from a subset of participants

A study physician will regularly review each participant's clinical, radiological, and microbiological results, including sputum findings, to assess disease progression or resolution. If a positive sputum result is identified at any time, the participant will be promptly contacted and referred for TB evaluation and treatment initiation in line with national guidelines. Referrals will be made for non-TB care as required. Ongoing contact will be maintained with all participants referred for TB treatment to encourage initiation of TB treatment and to continue to assess participant well-being until linkage to care and commencement of TB treatment is documented (verification by chart review or electronic record linkage). Individuals who commence TB treatment during follow-up will be considered to have reached the progression endpoint and will not continue with further TB-U cohort study visits.

Visit 1.5 will serve as the End-of-Study visit for participants in Sub-study 2. At this visit, clinically relevant results will be returned, participants will be counselled to seek clinical care if any symptoms or physical conditions worsen, and they will be thanked for their participation

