We will use survival analysis methods to estimate the time to progression. The primary progression endpoint will be defined as a positive sputum test. An alternative progression endpoint will include worsening of symptoms or clinical status, radiological progression and/or starting TB treatment. Person-time will be calculated from date of entry to the TB-U cohort until the earliest of date of the progression endpoint, the last visit seen, or death. Participants who have not met the progression endpoint by the end of follow-up will be censored administratively at the date of the 12-month visit. Since we expect <15% to progress (based on published data), we will use restricted mean survival time (RMST) to estimate the average survival over follow-up. We will use linear regression to compare log-transformed plasma biomarkers between progressors and non-progressors, assuming a normal distribution, or Wilcoxon rank sum tests if data are non-normally distributed. Biomarkers that are measured as binary variables will be compared between groups using Chi-squared tests. Factors associated with time to progression will be explored using Cox regression.

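### In the TB-U cohort, event-free time for the sputum endpoint ends at the last attended visit rather than the last visit with a sputum result, which can understate 12-month progression

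*Protocol*

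**What the plan says.** The operative text is the TB-U cohort paragraph of Protocol 5.2. It defines the endpoint: "The primary progression endpoint will be defined as a positive sputum test". It adds a second one: "An alternative progression endpoint will include worsening of symptoms or clinical status, radiological progression and/or starting TB treatment". A single person-time rule then follows for both, from cohort entry "until the earliest of date of the progression endpoint, the last visit seen, or death". Participants without the endpoint by the end of follow-up are "censored administratively at the date of the 12-month visit". Restricted mean survival time and Cox regression are the planned summaries of time to progression.

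Section 3.5 gives the context. Cohort visits take place "every three months (month 3,6,9 &12) for one year", with two sputum samples planned at each: "Sputum specimens will be collected for TB phenotyping, consisting of two samples, either an early-morning and spot specimen or two spot specimens". It gives no rule for a visit at which neither sample is obtained. At community screening the protocol does foresee this and provides a substitute: if, after coaching, "the participant is still unable or refuses to produce a 3ml sputum sample, a tongue swab will be collected for NAAT". In cohort follow-up, facemask and breath condensate samples come from a subset only (the first 100, Table 7 footnote) and are not part of the sputum endpoint.

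**The concern.** A sputum endpoint can be seen only where sputum is tested. An attended visit still brings symptoms, examination, chest X-ray and blood, so a participant can be seen at month 12 with no sputum result. Section 5.2 then counts that person as free of sputum progression to month 12, although nobody tested for it. Ending follow-up at the last attended visit suits the alternative endpoint, which can be assessed at any visit. It does not suit the sputum endpoint, yet both share the rule.

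The share of TB-U that becomes bacteriologically confirmed within a year is named in the Background as an unknown needed to guide screening, and the stage gate may resize the cohort on it. If untested time enters as event-free time, the estimated risk falls and mean progression-free time rises. In the Cox model, a factor associated with poor sputum production could look protective.

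**Working it through.** **Inputs from the protocol.** 500 participants per site and annual progression of 10% (95% CI 6.2-13.3), both from 5.1; visits at months 3, 6, 9 and 12, from 3.5.

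**Assumptions, because the protocol gives no figure.** Sputum is missing at 10, 20 or 30% of visits, or from 10, 20 or 30% of people. All visits are attended, the hazard is constant, and a progressor stays sputum-positive until sampled.

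**1. The plan's own figure.** 500 × 0.062 = 31 and 500 × 0.133 = 66.5, which reproduces the stated 31-66 progressors per site. At 10%, 500 × 0.10 = 50.

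**2. Scattered misses, unrelated to progression.** Let u be the share of visits without sputum. Progression is never seen if every remaining visit fails. With progression spread evenly over the four quarters, the undetected share is (u + u² + u³ + u⁴)/4:
- u = 10%: 0.1111/4 = 2.8%
- u = 20%: 0.2496/4 = 6.2%
- u = 30%: 0.4251/4 = 10.6%

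Under the stated rule everyone undetected is carried to month 12 as event-free, so the estimate is 10% × (1 − share) = 9.7, 9.4 and 8.9%. Simulation with a constant hazard, which puts slightly more events early, gives 9.7, 9.4 and 9.0%.

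**3. Persistent non-producers, unrelated to progression.** If a share v gives no sputum at any follow-up visit, the stated rule gives 10% × (1 − v) = 9.0, 8.0 and 7.0%.

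At 20% missing, the progressors detected per site are about 47 in step 2 (500 × 0.094) and 40 in step 3 (500 × 0.080), instead of 50. The relative shortfalls are essentially the same at 6.2% and 13.3%.

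**4. Censoring at the last sputum result, same settings.** Simulation gives 10.0-10.3% for scattered misses and 10.0% for persistent non-producers.

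**5. Only non-progressors fail to produce.** All progressors are detected, so the stated rule gives 10%. Censoring at the last sputum result removes the non-producers from the risk sets and gives 0.10/[0.10 + 0.90 × (1 − v)]:
- v = 10%: 0.10/0.91 = 11.0%
- v = 20%: 0.10/0.82 = 12.2%
- v = 30%: 0.10/0.73 = 13.7%

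**6. Only progressors fail to produce.** With v = 20% of progressors, the stated rule gives 8.0% and the alternative gives 0.08/(0.08 + 0.90) = 8.2%. Both are too low.

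**7. Sampling error for scale.** At 10% of 500, the 95% half-width is 1.96 × √(0.10 × 0.90/500) = 2.6 percentage points.

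**The case against.** The strongest reply is that sputum is scheduled at every cohort visit, so if the schedule is followed the last visit attended is also the last visit with sputum. Handling of a missed assessment is often left to the statistical analysis plan, which is not at hand. Part of this stands: with no missed sputum there is no bias. But 5.2 is not silent. It fixes a stopping date, and that date does not depend on the test that defines the endpoint.

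The second reply is that the evidence for sputum failure comes from household screening, whereas Table 1 admits to the cohort only people with three sputum results. A visit is also uninformative only if both samples fail. This stands, and it limits the size: the 10-30% is assumed. Scattered misses shift the estimate by 0.3-1.0 points, against a sampling half-width of 2.6 points.

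The third reply is that visits without sputum are not blind. The alternative endpoint covers clinical and radiological worsening and treatment start, and 3.5 counts starting TB treatment as reaching the progression endpoint. Some missed cases would be caught this way. However, 5.2 places treatment start only in the alternative endpoint, so the two sections need reconciling before this can be relied on.

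A reader might infer that progression will be understated, or that censoring at the last sputum result is correct whatever the reason for missing sputum. The document supports neither. The direction in steps 2 and 3 requires missingness unrelated to progression. In step 5 the present rule is right and the replacement overstates. Larger losses can be produced by assuming that people stop producing for good at each visit (6.0% at 20% per visit), but nothing in the protocol supports such a pattern.

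**Conclusion.** The mismatch is real: a sputum endpoint is paired with a stopping date that does not require sputum. If visits without sputum fall at the end of follow-up and are unrelated to progression, a true 12-month risk of 10% is estimated at about 9.7-9.0% (scattered misses) or 9.0-7.0% (persistent non-producers) for an assumed 10-30% missing. The actual size cannot be read from the protocol and may be small, given that entrants produced sputum at entry.

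The two stopping rules bracket the truth for patterns between missingness unrelated to progression and missingness confined to non-progressors, apart from the slight upward drift in step 4. They do not bracket it if progressors are the ones more likely to fail. The point concerns a sub-study 2 estimate; the co-primary IGRA comparisons are unaffected. It is worth correcting because the correction is cheap.

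**What to change.** In 5.2, for the primary sputum endpoint, end event-free person-time at the last visit with at least one valid sputum Xpert or MGIT result. Keep the last attended visit as the stopping point for the alternative clinical and radiological endpoint. Report how many attended visits gave no sputum result, and how many participants gave none during follow-up. Repeat the primary estimate under the present rule as a sensitivity analysis and show the two together. In the same edit, reconcile 3.5 and 5.2 on whether starting TB treatment counts towards the primary or only the alternative endpoint.

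The stopping rule itself takes one sentence in 5.2, carried into the statistical analysis plan. It needs no new data; the cost is slightly less person-time and one extra analysis.
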